#### 13.2.2 Background Data

The investigator shall supply the Sponsor, on request, with any required background data from the study documentation or clinic records. This is particularly important when CRFs are illegible or when errors in data transcription are suspected. In case of special problems and/or governmental queries or requests for audit inspections, it is also necessary to have access to the complete study records, provided that subject confidentiality is protected.

#### 13.2.3 Audits and Inspections

An audit is a systematic and independent examination of trial related activities and documents to determine whether the evaluated trial related activities were conducted, and the data were recorded, analyzed and accurately reported according to the protocol, Immuron' SOPs and those of their designees, GCP and the applicable regulatory requirement(s).

Authorized representatives of Immuron, its designee, a regulatory authority, or the IRB/IEC may visit the center to perform audits or inspections. The investigator should contact Immuron immediately if they are contacted by a regulatory agency about an inspection at their center. If an audit or inspection occurs, the PI and institution agree to allow the auditor/inspector direct access to all relevant documents and allocate their time and the time of their staff to the auditor/inspector to discuss findings and any relevant issues.

#### 13.2.4 Case Report Forms

For each subject who provides consent, CRFs must be completed and be signed by the principal investigator or co-investigator. This also applies to records for those subjects who fail to complete the study (even during the screening period if a CRF was initiated). If a subject withdraws from the study, the reason must be recorded on the CRF. If a subject is withdrawn from the study because of a treatment-limiting AE, thorough efforts should be made to clearly document the outcome.

All forms should be typed or filled out using a black ball-point pen, and must be legible. Errors should be crossed out but not obliterated, the correction inserted, and the change initialed and dated by the investigator or his/her authorized delegate. The CRFs, as well as the protocol, are confidential. The CRFs remain the property of the sponsor at all times.

### 13.3 Monitoring the Study

In accordance with ICH GCP guidelines, the study monitor must have direct access to the investigator's source documentation in order to verify the data recorded in the CRFs for consistency.

It is understood that the responsible Sponsor monitor, as a Immuron representative, will contact and visit the investigator regularly and that he/she will be allowed, on request, to inspect the various records of the trial (CRFs and other pertinent data) provided that subject confidentiality is maintained in accord with local requirements.

It will be the monitor's responsibility to inspect the CRFs at regular intervals throughout the study, to verify the adherence to the protocol and the completeness, consistency and accuracy of the data being entered on them. The PI agrees to allow the monitor direct access to all relevant documents and to allocate his/her time and the time of his/her staff to the monitor to discuss findings and any relevant issues.

### **13.4 Confidentiality of Trial Documents and Subject Records**

The investigator must assure the subjects' anonymity will be maintained and that their identities are protected from unauthorized parties. On CRFs or other documents submitted to the Sponsor, subjects should not be identified by their names, but by the subject's initials and an identification code. The investigator should keep a subject identification log showing codes, names and addresses. Documents not for submission to Immuron (e.g. subject's written consent forms, identification log), should be maintained by the investigator in strict confidence.

All information concerning the study treatment and the Sponsor company and its operation, such as patent applications, formulae, manufacturing processes, basic scientific data and material not previously published are considered confidential and shall remain the sole property of the Sponsor. The investigator agrees to use this information only in accomplishing the study and will not use it for any other purposes without written consent from the Sponsor.

### **13.5 Publication of Data and Protection of Trade Secrets**

In accord with standard editorial and ethical practice, Immuron will support publication of multicenter trials only in their entirety and not as individual site data.

The results of this study may be published or presented at scientific meetings. If this is envisaged, the investigator agrees to submit all manuscripts or abstracts to Immuron prior to submission. This allows the Sponsor to protect proprietary information and to provide comments based on information from other studies that may not yet be available to the investigator.

Any formal publication of the study in which input of Immuron personnel exceeded that of conventional monitoring will be considered as a joint publication by the investigator and the appropriate Immuron personnel. Authorship will be determined by an mutual agreement prior to the start of the study. The number of subjects enrolled will be taken into consideration in the selection of authors. Additional authors will be agreed prior to the completion of the study. Investigators who do not enroll any subjects into the study will not be included in this list.

### **13.6 Anticipated Subject Accrual and Duration of the Study**

It is anticipated that recruitment of subjects will take approximately 12 months form initiation of the first study site. The investigator should continually compare the actual and expected accrual rates, and make every effort to ensure that they are as closely matched as possible. If the investigator anticipates major problems with recruitment, or delay in the expected completion date, he/she should discuss this with Immuron as early as possible.

15. APPENDICES

## APPENDIX A ADVERSE EVENT TOXICITY GRADING SCALES

The following toxicity grading scales (TGS) have been adapted from the *FDA Guidelines for Toxicity Grading Scales for healthy adult and adolescent volunteers involved in clinical studies of preventive vaccines*. The parameters described in the tables below provide further information on which to base assessment of the severity for AEs which may be reported in this study. These include vital signs, gastrointestinal and other systemic events and clinical laboratory tests. These guidelines should be reviewed in the context of the values measured at Screening and Baseline.

These TGS do not address all potential adverse events. All other adverse events reported during the study must be recorded, including an assessment of severity as described in Section 10.2.2 (Table 8) of this protocol.

### Clinical abnormalities

Vital Signs *	Mild (Grade 1)	Moderate(Grade 2)	Severe (Grade 3)	Potentially Life Threatening (Grade 4)
Fever (°C) ** (°F) **	38.0 – 38.4 100.4 – 101.1	38.5 – 38.9 101.2 – 102.0	39.0 – 40 102.1 – 104	> 40 > 104
Tachycardia - beats per minute	101 – 115	116 – 130	> 130	Emergency Room (ER) visit or hospitalization for arrhythmia
Bradycardia - beats per minute***	50 – 54	45 – 49	< 45	ER visit or hospitalization for arrhythmia
Hypertension (systolic) - mm Hg	141 – 150	151 – 155	> 155	ER visit or hospitalization for malignant hypertension
Hypertension (diastolic) - mm Hg	91 – 95	96 – 100	> 100	ER visit or hospitalization for malignant hypertension
Hypotension (systolic) – mm Hg	85 – 89	80 – 84	< 80	ER visit or hospitalization for hypotensive shock
Respiratory Rate – breaths per minute	17 – 20	21 – 25	> 25	Intubation

- \* Subject should be at rest for all vital sign measurements.
- \*\*Oral temperature; no recent hot or cold beverages or smoking.
- \*\*\* When resting heart rate is between 60 – 100 beats per minute. Use clinical judgement when characterizing bradycardia among some healthy subject populations, for example, conditioned athletes

## APPENDIX A - Clinical abnormalities, continued

Systemic General	Mild (Grade 1)	Moderate (Grade 2)	Severe (Grade 3)	Potentially Life Threatening (Grade 4)
Nausea/vomiting	No interference with activity or 1 - 2 episodes/24 hours	Some interference with activity or > 2 episodes/24 hours	Prevents daily activity, requires outpatient IV hydration	ER visit or hospitalization for hypotensive shock
Diarrhea	2 - 3 loose stools or < 400 gms/24 hours	4 - 5 stools or 400 - 800 grams/24 hours	6 or more watery stools or > 800gms/24 hours or requires outpatient IV hydration	ER visit or hospitalization
Headache	No interference with activity	Repeated use of non-narcotic pain reliever > 24 hours or some interference with activity	Significant; any use of narcotic pain reliever or prevents daily activity	ER visit or hospitalization
Fatigue	No interference with activity	Some interference with activity	Significant; prevents daily activity	ER visit or hospitalization
Myalgia	No interference with activity	Some interference with activity	Significant; prevents daily activity	ER visit or hospitalization

Systemic Illness	Mild (Grade 1)	Moderate (Grade 2)	Severe (Grade 3)	Potentially Life Threatening (Grade 4)
Illness or clinical adverse event (as defined according to applicable regulations)	No interference with activity	Some interference with activity not requiring medical intervention	Prevents daily activity and requires medical intervention	ER visit or hospitalization

**APPENDIX A - Laboratory Abnormalities**

Serum	Mild (Grade 1)	Moderate (Grade 2)	Severe (Grade 3)	Potentially Life Threatening (Grade 4)**
Sodium – Hypernatremia mEq/L	132 – 134	130 – 131	125 – 129	< 125
Sodium – Hypernatremia mEq/L	144 – 145	146 – 147	148 – 150	> 150
Potassium – Hyperkalemia mEq/L	5.1 – 5.2	5.3 – 5.4	5.5 – 5.6	> 5.6
Potassium – Hypokalemia mEq/L	3.5 – 3.6	3.3 – 3.4	3.1 – 3.2	< 3.1
Glucose – Hypoglycemia mg/dL	65 – 69	55 – 64	45 – 54	< 45
Glucose – Hyperglycemia Fasting – mg/dL Random – mg/dL	100 – 110 110 – 125	111 – 125 126 – 200	>125 >200	Insulin requirements or hyperosmolar coma
Blood Urea Nitrogen BUN mg/dL	23-26	27 – 31	> 31	Requires dialysis
Creatinine – mg/dL	1.5 – 1.7	1.8 – 2.0	2.1 – 2.5	> 2.5 or requires dialysis
Calcium – hypocalcemia mg/dL	8.0 – 8.4	7.5 – 7.9	7.0 – 7.4	< 7.0
Calcium – hypercalcemia mg/dL	10.5 – 11.0	11.1 – 11.5	11.6 – 12.0	> 12.0
Magnesium – hypomagnesemia mg/dL	1.3 – 1.5	1.1 – 1.2	0.9 – 1.0	< 0.9
Phosphorous – hypophosphatemia mg/dL	2.3 – 2.5	2.0 – 2.2	1.6 – 1.9	< 1.6
CPK – mg/dL	1.25 – 1.5 x ULN	1.6 – 3.0 x ULN	3.1 –10 x ULN	> 10 x ULN
Albumin – Hypoalbuminemia g/dL	2.8 – 3.1	2.5 – 2.7	< 2.5	--

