## 14. Concurrent medications including:

- Anti-NASH therapy(s) taken for more than 10 continuous days in the last 3 months. These include S-adenosyl methionine (SAM-e), betaine, milk thistle, bacterial probiotic supplements (other than yoghurt or other natural food sources), vitamin E and gemfibrozil.
  - NOTE: If determinant biopsy is performed while on stable treatment – subject is eligible;
  - Wash out for any of the anti-NASH therapies is as follow: under 10 days no washout required, more than 10 days and up to 3 months treatment requires 6 weeks washout. Any treatment of over 3 months would require to re-biopsy to ensure histological eligibility
  - Thiazolidinediones (glitazones), dipeptidyl peptidase 4 inhibitors (gliptins) or glucagon-like peptide-1 analogs in the last 6 months.  
NOTE: if determinant biopsy is performed while on stable treatment of at least 6 months – subject is eligible.
  - NOTE: Allowable anti-diabetic treatment includes metformin and/or sulfonylureas administered at constant dose for at least 2 months prior to study entry
  - NOTE: Subjects treated with Insulin are eligible if clinically stable on insulin treatment (i.e. no recurrent acute hypo-/hyperglycemic episodes diagnosed clinically and by Glucose serum levels of <50 mg/dL and >200 mg/dL respectively) for at least 2 months prior to study entry
- immune modulatory agents including:
  - Within 3 months of study entry:
    - systemic steroids for more than 7 days
    - daily treatment with multiple non-steroidal anti-inflammatory drugs (such as aspirin >100mg/day, ibuprofen, naproxen, meloxicam, celecoxib) for more than 1 month
  - In the last 12 months:
    - azathioprine, 6-mercaptopurine, methotrexate, cyclosporin, anti-TNF $\alpha$  therapies (infliximab, adalimumab, etanercept) or anti-integrin therapies (namixilab)
- more than 10 consecutive days oral or parenteral antibiotics within 4 weeks prior to study entry NOTE: subjects administered with antibiotics for more the 5 days prior to study entry would not be included in the stool and PBMC analysis)
- Variable dose of anti-lipidemic agents (HMG Co-A reductase inhibitors – “statins”) in the 3 months prior to Screening

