## 15. The following laboratory abnormalities:

- Neutrophil count  $\leq 1.0 \times 10^9/L$
- Platelets  $<100 \times 10^9/L$
- Hemoglobin  $<10g/dL$
- Albumin  $< 3.5g/dL$
- International Normalized Ratio (INR)  $>1.5$
- Total bilirubin  $>1.5$  x upper limit of reference range (unless Gilbert’s syndrome or extrahepatic source as denoted by increased indirect bilirubin fraction)
- Either creatinine clearance  $\leq 60$  mL/minute calculated by Cockcroft-Gault or creatinine  $>1.5$ x upper limit of reference range (see Section 6.4.2).

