#### 9.2.2 During the Study Dosing Period

Throughout the study medication dosing period, subjects may not receive any of the following concomitant medications:

- other anti-NASH therapy(s) including, SAM-e, betaine, milk thistle and probiotic supplements (not including yoghurt);
- thiazolidinediones (glitazones), dipeptidyl peptidase 4 inhibitors (gliptins) or GLP-1 analogs, unless the subject was recruited on a stable dose.
- Allowable anti-diabetic treatment includes insulin, metformin and/or sulfonylureas administered at constant dose for at least 2 months prior to study entry;
- immune modulatory agents including
  - systemic steroids for more than 7 days
  - multiple non-steroidal anti-inflammatory drugs such as aspirin (>100mg/day), ibuprofen, naproxen, meloxicam, celecoxib;
  - azathioprine, 6-mercaptopurine, methotrexate, cyclosporin, anti-TNF $\alpha$  therapies (infliximab, adalimumab, etanercept) or anti-integrin therapies (namixilab).

Treatment with antilipidemic agents (HMG Co-A reductase inhibitors – “statins”), vitamin E, gemfibrozil and allowable antidiabetic treatment (metformin and/or sulfonylurea) must be stable throughout the study.

Antibiotics should be taken if clinically indicated but avoided where possible.

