#### 10.6 Guidance for Discontinuation of Treatment

To date, no specific toxicities have been identified that result from IMM-124E treatment. Any toxicities and/or abnormal laboratory findings should be investigated for etiology and graded according to Table 8 ([Section 10.2.1](#)) and [Appendix A](#).

The following toxicity management will be followed:

**Grade 1 or 2:** Patients may continue study drug.

**Grade 3:** Patients with any Grade 3 toxicity considered to be at least possibly related to treatment (i.e. treatment related events) should be evaluated carefully by the investigator prior to continuing study drug. Investigators may discuss individual cases with the Medical Monitor.

**Grade 4:** Patients developing any Grade 4 toxicity should have treatment interrupted, unless the Grade 4 toxicity is clearly unrelated to study drug and continued treatment does not pose a serious risk to the patient. After the event has returned to normal or baseline levels, study drug may be re-started. If the toxicity re-appears, the investigator should contact the Medical Monitor to discuss the subject's withdrawal.

For any subject experiencing any event (irrespective of severity) which, in the opinion of the Investigator, contraindicates further dosing in that subject and the event is considered to be at least possibly related to treatment (or where causality to study treatment cannot be ruled out – see [Section 10.2.1](#)), continued dosing of the subject should be interrupted. In all cases, the final treatment decisions, made in response to toxicity, are the responsibility of the Principal Investigator. A careful evaluation of the potential risk/benefit will dictate the optimal therapeutic course. Should treatment be interrupted, re-initiation will follow review of the available safety data and in agreement with the Sponsor. There will be no dose reduction or modification.

If the investigator deems that management of the patient's medical condition requires knowledge of the study treatment regimen, then the Medical Monitor must be contacted for consultation and the procedures described in [Section 8.2](#) followed. If a patient dies from an event that is considered to be at least possibly related to treatment, continued dosing of all study participants should be interrupted:

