### 12.6.2 Clinical Laboratory Parameters

Routine samples are being collected for assessment of clinical chemistry and hematology. Summary tables at each time point and by toxicity grade will be presented by dose level. All data will be listed.

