**APPENDIX A – Laboratory Abnormalities, continued**

Serum	Mild (Grade 1)	Moderate (Grade 2)	Severe (Grade 3)	Potentially Life Threatening (Grade 4)**
Total Protein – Hypoproteinemia g/dL	5.5 – 6.0	5.0 – 5.4	< 5.0	--
Alkaline phosphate – increase by factor	1.1 – 2.0 x ULN	2.1 – 3.0 x ULN	3.1 – 10 x ULN	> 10 x ULN
Liver Function Tests –ALT, AST increase by factor	1.1 – 2.5 x ULN	2.6 – 5.0 x ULN	5.1 – 10 x ULN	> 10 x ULN
Bilirubin – when accompanied by any increase in Liver Function Test increase by factor	1.1 – 1.25 x ULN	1.26 – 1.5 x ULN	1.51 – 1.75 x ULN	> 1.75 x ULN
Bilirubin – when Liver Function Test is normal; increase by factor	1.1 – 1.5 x ULN	1.6 – 2.0 x ULN	2.0 – 3.0 x ULN	> 3.0 x ULN
Cholesterol	201 – 210	211 – 225	> 226	---
Pancreatic enzymes – amylase, lipase	1.1 – 1.5 x ULN	1.6 – 2.0 x ULN	2.1 – 5.0 x ULN	> 5.0 x ULN

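### Appendix A assigns Grade 3 or 4 to states the entry criteria allow at Baseline, and neither the grading instruction nor the protocol's by-grade laboratory tables say how a Baseline grade is handled

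*Protocol*

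**What the plan says.** **Grading scale.** The introduction to Protocol Appendix A says the scale was adapted from one for healthy volunteers in preventive vaccine studies, and asks that grades be considered in the context of Screening and Baseline values. In the hyperglycaemia row, fasting glucose above 125 mg/dL is Grade 3 and Grade 4 reads "Insulin requirements or hyperosmolar coma". In the row "Bilirubin – when accompanied by any increase in Liver Function Test increase by factor", 1.51-1.75 x ULN is Grade 3 and anything above 1.75 x ULN is Grade 4.

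**Entry and concomitant treatment.** Section 6.3, criterion 14: "Subjects treated with Insulin are eligible if clinically stable on insulin treatment". Section 9.2.2, for the dosing period: "Allowable anti-diabetic treatment includes insulin, metformin and/or sulfonylureas administered at constant dose for at least 2 months prior to study entry". Section 6.3, criterion 15, excludes bilirubin above 1.5 x ULN unless there is Gilbert's syndrome or an "extrahepatic source as denoted by increased indirect bilirubin fraction". Section 6.2 admits HbA1c up to 9.0.

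**Use of the grades.** Section 10.6: "Patients developing any Grade 4 toxicity should have treatment interrupted", with an exemption for a toxicity clearly unrelated to study drug where continuing poses no serious risk. Section 12.6.2: "Summary tables at each time point and by toxicity grade will be presented by dose level".

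**SAP.** Section 8.5 plans change-from-Baseline summaries and shift tables on normal, abnormal and clinically significant values. The table list in Section 12 contains no laboratory table by toxicity grade.

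**The concern.** The scale was built for people without diabetes or liver disease, and this trial recruits people with both. Some subjects can therefore meet a Grade 3 or 4 criterion on Day 0, before any study drug, and go on meeting it at every visit.

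Two things are at stake. First, consistency of grading: if the documents do not say what to do with a grade already present at Baseline, two sites can grade the same patient differently. Second, readability of the safety tables: adverse-event severity and changes in laboratory parameters are both part of the primary safety endpoint (Section 4.2). A by-grade table that carries Baseline status gives a background count in every arm, against which a modest drug effect is harder to see.

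**Working it through.** The plan states no figure on this point, so there is nothing to reproduce. The check applies the Appendix A bands to states the entry criteria allow, then reads the rules that use the grades.

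**1. Insulin.** The Grade 4 cell has no qualifier such as new or increased. Read literally, an eligible insulin user meets it at Baseline and at each later visit.

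**2. Bilirubin.** Bands from Appendix A:

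| Bilirubin (x ULN) | Grade, liver test raised | Grade, liver tests normal | Eligible without Gilbert's or raised indirect fraction |
|---|---|---|---|
| 1.5 | 2 | 1 | yes |
| 1.6 | 3 | 2 | no |
| 1.76 | 4 | 2 | no |
| 2.5 | 4 | 3 | no |
| 3.1 | 4 | 4 | no |

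An ordinary entrant reaches Grade 2 at most at entry. A Gilbert's entrant with a raised liver test can enter at Grade 3 or 4, since the exception sets no upper limit.

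**3. Fasting glucose.** The documents give no distribution. Assume, for the stratum with HbA1c above 6.0, a lognormal with mean m and SD s. Then σ² = ln(1 + s²/m²), μ = ln(m) − σ²/2, and P(glucose > 125) = 1 − Φ((ln 125 − μ)/σ).

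| Assumed mean (mg/dL) | SD 25 | SD 40 |
|---|---|---|
| 120 | 0.38 | 0.39 |
| 135 | 0.63 | 0.55 |
| 150 | 0.85 | 0.71 |

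These are illustrations only. The stratum begins just above HbA1c 6.0 and includes pre-diabetes, so a lower mean, and a lower proportion, is possible.

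**4. Does the Grade 4 rule fire on these patients?** Not automatically. Section 10.6 concerns patients *developing* a toxicity, exempts one clearly unrelated to study drug where continuing poses no serious risk, and allows restart at normal or baseline levels. Section 10.2 excludes unchanged pre-existing conditions from adverse events. Section 10.5 generally keeps symptom-free laboratory findings out unless clinically significant. What is missing is an operational rule: Appendix A asks for Baseline context without saying how it alters a grade.

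**5. Tables.** The protections in step 4 concern adverse events and management. Section 12.6.2 concerns laboratory values and has no Baseline-relative condition, so the states in steps 1-3 would be counted at each time point. The SAP's tables are Baseline-relative but do not use toxicity grades. SAP Section 10 leaves changes from the protocol to the study report, so the SAP does not itself say that the by-grade tables are dropped.

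**6. Size, insulin only.** The insulin share p is not given. With 40 per arm, the expected count is 40p per arm and 120p overall. Chance imbalance between two arms is P(|X − Y| ≥ 4), with X and Y independent Binomial(40, p).

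| Assumed p | Per arm of 40 | Of 120 | P(two arms differ by 4 or more) |
|---|---|---|---|
| 5% | 2 | 6 | 0.07 |
| 10% | 4 | 12 | 0.19 |
| 20% | 8 | 24 | 0.33 |

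This ignores stratification by HbA1c, which should reduce the imbalance.

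**The case against.** The strongest reply is that Baseline is already addressed in several places: the wording of Section 10.6, its exemption, the adverse-event definition in Section 10.2 and the introduction to Appendix A. This stands against a stronger claim that a reader might infer, namely that eligible insulin users or Gilbert's patients would have treatment interrupted simply for being enrolled. The documents do not support that claim.

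It is also fair to say that the insulin cell sits in the hyperglycaemia row and can be read as hyperglycaemia severe enough to need insulin. A stable user with normal fasting glucose would then have nothing to grade. That reading is tenable, so the counts in step 6 hold only on the literal one. That both readings are open is itself a reason to clarify the text.

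Nor would it be right to say that no table is relative to Baseline, because SAP Section 8.5 provides such tables. The problem is confined to Protocol 12.6.2 and its mismatch with the SAP.

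A contrast between the fasting Grade 3 limit of 125 mg/dL and the 200 mg/dL in the insulin entry note should not be pressed. The note defines acute episodes for eligibility and does not specify fasting, and Appendix A's random-glucose line uses the same 200 mg/dL for Grade 3.

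What the reply leaves standing is the absence of an operational rule in Appendix A and of a Baseline-relative condition in 12.6.2.

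**Conclusion.** The point holds in a limited form. Appendix A gives Grade 3 or 4 to states allowed at entry, its Baseline instruction cannot be applied uniformly as written, and the protocol's by-grade laboratory tables would include those states in every arm. The SAP plans different tables without saying that the by-grade ones are withdrawn.

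The consequence is noise and dilution. A reader might infer that the grade counts would chiefly reflect eligibility and conceal any true signal. The documents do not show that: randomisation prevents systematic bias between arms, and the change-from-Baseline and shift tables remain.

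The size is unknown. The figure of 6-24 of 120 subjects rests on an assumed 5-20% insulin share and the literal reading of the cell. The glucose range of 38-85% rests on an assumed distribution. No frequency can be given for Gilbert's syndrome combined with a raised liver test.

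**What to change.** **Patient management.** The sponsor must reconcile Protocol Section 6.3 (criteria 14 and 15), Section 9.2.2, Section 10.6 and Appendix A (introduction, hyperglycaemia row and bilirubin rows), stating how a grade already present at Baseline is handled. No clinical threshold or rule is proposed here.

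**Analysis.** Align Protocol 12.6.2 with SAP 8.5. Where toxicity grades are tabulated, count a subject only if the post-baseline grade exceeds that subject's own Baseline grade, for example in a table of Baseline grade against worst post-baseline grade by arm. Count the insulin criterion only where insulin was not in use at Baseline. Otherwise, on the literal reading, a Baseline user starts at Grade 4 and could never show a higher glucose grade.

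Keep the SAP's change-from-Baseline summaries alongside, because a subject whose bilirubin is already Grade 4 at Baseline cannot move up a grade.

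**Cost.** Some wording, slightly more programming, and fewer Grade 3-4 laboratory entries on display. Raw values stay in the listings.
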